### **B-2.7.1. Acceptance criteria and sample size considerations**

In studies supporting FDA 510(k) applications for the predicate device (JM-103), correlation coefficients ranged from 0.84 – 0.946. Based on these studies, the acceptance criterion for demonstrating that BiliCam has comparable accuracy as the predicate device is: the lower limit of the 2-sided 95% CI around the point estimate for the correlation coefficient for the entire group of evaluable subjects will be  $\geq 0.83$ .

It is planned to continue enrollment until 225 subjects (75 at each site) complete all study procedures (as defined in section B-2.1). It is possible that data on BCB and/or TSB measurements may not be available on a limited number of subjects who complete the study because of a laboratory issue with the TSB (e.g. specimen too hemolyzed for assay) or because of problem with the BCB value (e.g. out of range). The sample size of 225 enrolled subjects will ensure that paired BCB-TSB levels will be available on a minimum of 200 evaluable subjects for the primary analysis (correlation between paired BCB-TSB levels). Based on previous studies of BiliCam, it is estimated that the underlying true population correlation between BCB and TSB measurements is  $\geq 0.90$ . With a sample size of 200 evaluable subjects, the chance for the lower limit of the 95% CI for the

observed correlation to be  $\geq 0.83$  is higher than 95%.

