## **B-2.1. Sample size**

It is planned to have 225 subjects complete study procedures, defined as having blood drawn for a TSB level and valid BiliCam images obtained, with the goal of collecting data on  $\geq$  200 newborns who have paired BCB and TSB data available for the primary analyses. As described in section B-2.2, at each study site, one of two enrollment plans will be used: “Simultaneous” (in which enrollment and the study visit will occur at one time-point), or “Staged” (in which the study visit occurs at a later time from enrollment). At sites using the Staged enrollment plan, a proportion of subjects who are enrolled will not complete study procedures because: 1) they

become ineligible because of the occurrence of an exclusion criterion after enrollment, but before the study visit occurs, 2) parents withdraw consent, or 3) subject does not return for the study visit. At these sites, up to 150 subjects will be enrolled and enrollment will be discontinued when a maximum of 75 newborns at the site have completed study procedures. At sites using the Simultaneous enrollment plan, because all subjects are expected to have completed study procedures, up to a maximum of 75 subjects will be enrolled.

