## **B-2.2. Enrollment plan**

The goal of the enrollment plan is to obtain data on newborns across the entire measuring range of BiliCam (0-20 mg/dL) while oversampling newborns with high TSB levels. The use of two enrollment plans will enable this distribution. At sites using the Simultaneous enrollment plan, newborns will be enrolled at the time (within 2 hours) that blood is being obtained for a TSB level because the newborn is clinically jaundiced (i.e. the TSB is being ordered for clinical purposes). Thus, enrollment and the study visit will occur simultaneously. At Staged enrollment plan sites, subjects will be enrolled prior to being 48 hours old; these subjects will have a study visit after they are 48 hours old (i.e. the enrollment and the study visit will occur at different times). For these subjects, blood will be obtained for a TSB level as part of the study at the study visit.

A subject will be considered to be enrolled in the study once the consent is signed by his/her parent. Once enrolled, a subject's participation will be documented on the study case report forms and the subject will be included in the analyses of study data.

Enrollment procedures are described in detail below.

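### Does the sentence in B-2.7.1 that 225 enrolled subjects secure 200 evaluable pairs leave the trial short of its planned sample size?

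*Combined protocol and SAP*

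**What the plan says.** B-2.1 sets the target: "It is planned to have 225 subjects complete study procedures", completion being "defined as having blood drawn for a TSB level and valid BiliCam images obtained". It treats 200 or more paired values as an aim, introduced by "with the goal of collecting data on".

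The sample-size paragraph of B-2.7.1 opens on the same basis: "It is planned to continue enrollment until 225 subjects (75 at each site) complete all study procedures (as defined in section B-2.1". It then concedes that values "may not be available on a limited number of subjects who complete the study", naming a hemolyzed specimen and an out-of-range BiliCam result as examples. The next sentence changes both the unit and the strength of the claim: "The sample size of 225 enrolled subjects will ensure that paired BCB-TSB levels will be available on a minimum of 200 evaluable subjects". The paragraph ends with a power above 95% for 200 evaluable subjects.

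Under B-2.2 a subject is enrolled at signed consent. C-2.0 caps enrollment at 375 and ends it at 225 completers. For Staged sites, B-2.1 says "enrollment will be discontinued when a maximum of 75 newborns at the site have completed study procedures", whereas C-2.0 attaches a less-than sign to the 75.

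**The concern.** Enrolled and completed are different counts here. B-2.1 expects some Staged-site subjects to drop out between consent and the study visit, and the 375 ceiling allows for many of them. If recruitment really ended at 225 consents, completers could fall well below 200. Taking the ceiling as a completion rate, 225/375 = 60%, 225 consents would give 225 × 0.60 = 135 completers, with power of about 90%.

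Even counted in completers, the promise of 200 is firmer than its support. A completer can still lack a pair because the sample was unusable, the server returned nothing, or the BiliCam result was above 20.0 (B-2.3.2). The last cannot be assumed rare, because B-2.2 plans on "oversampling newborns with high TSB levels". No loss rate is given, and enrollment is not tied to the number of pairs.

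Finally, the Staged-site condition in C-2.0, read literally, is already met at zero completers. Read as at most 74 per Staged site, three sites cannot reach 225. At stake would be the evaluable number on which the power statement rests.

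**Working it through.** **1. The plan's own power figure.** Inputs from B-2.7 and B-2.7.1: lower limit of the two-sided 95% CI for Pearson's r at least 0.83, true r = 0.90, n = 200. By Fisher's z:

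power = Φ[(atanh 0.90 − atanh 0.83) × √(n − 3) − 1.96]

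atanh 0.90 = 1.4722 and atanh 0.83 = 1.1881, a difference of 0.2841. With √197 = 14.036, power = Φ(3.987 − 1.960) = Φ(2.027) = 97.9%. A bivariate-normal simulation of 100,000 runs gives 98.0%. The stated figure of more than 95% is reproduced.

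**2. What the margin covers.** 225 − 200 = 25, and 25/225 = 11.1%. The documents give no missing-pair rate, so the rates below are assumptions. The number of pairs is taken as Binomial(225, 1 − loss).

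| Assumed loss | Expected pairs | P(at least 200 pairs) | Power averaged over the number of pairs |
|---|---|---|---|
| 5% | 213.75 | >99.9% | 98.5% |
| 8% | 207 | 96% | 98.2% |
| 10% | 202.5 | 75% | 98.0% |
| 15% | 191.25 | 6% | 97.3% |

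A 95% assurance of 200 pairs needs a loss of at most about 8.2%. So 200 is not guaranteed, but power hardly moves over this range.

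**3. How far the power claim stretches.** Same formula:

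| Pairs | Power |
|---|---|
| 225 | 98.8% |
| 200 | 97.9% |
| 190 | 97.3% |
| 180 | 96.6% |
| 165 | 95.1% |
| 150 | 93.1% |

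The claim holds down to 165 pairs, that is, with 60 of 225 completers lost (26.7%).

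**4. Which unit governs recruitment.** Three statements count completers: B-2.1, the opening of the sample-size paragraph in B-2.7.1, and the stop in C-2.0. One clause says enrolled, and it describes what the sample will yield; it is not a rule for ending recruitment. The enrollment ceiling also presupposes completers: 375 = 150 + 150 + 75 matches two Staged sites and one Simultaneous site, and would make no sense if recruitment ended at 225 consents. The 135-completer case therefore cannot arise under the stated stop. It also treats a ceiling as an expected completion rate, which the plan never gives.

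**5. The Staged-site stop.** Read as at most 74 per Staged site, two Staged sites and one Simultaneous site give 74 + 74 + 75 = 223, and three Staged sites give 222. Both contradict the 225 in C-2.0 itself and the 75 per site in B-2.7.1. Only the B-2.1 reading, up to 75 per site, is consistent: 3 × 75 = 225.

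**The case for a change.** The best case for acting is that this sentence is the plan's only link between recruitment and the 200 behind the power claim. It uses a term the plan defines otherwise, it contradicts the sentence before it, and correcting it costs a few words. If fewer than 200 pairs result, the trial misses a minimum it set itself.

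The textual part of this stands: the unit is wrong, and the promise is stronger than the aim in B-2.1. The Staged-site passages in B-2.1 and C-2.0 do conflict as printed, although a less-than-or-equal sign that lost its bar in text extraction would explain it. The exit form (B-2.5) also omits the requirement that images be valid. If that form feeds the 225 count, a few more completers could lack a pair, but they draw on the same 25-subject margin.

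The practical part does not stand. A pair count somewhat under 200 leaves the acceptance criterion and the analysis as they are, because B-2.7 analyzes all subjects with paired values, however many there are. A rewritten sentence saying that 200 pairs are expected if no more than 25 are lost would only restate 225 − 25 = 200.

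One caution concerns step 3: it changes n and holds r at 0.90. Dropping results above 20.0 truncates the range and could change r itself, by an amount the documents do not let one estimate. Rewording the enrollment sentence would not affect that.

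**Conclusion.** The concern is right about the wording but calls for no change to the plan. *Enrolled* is a clerical slip for *completing*, the promise of 200 is an overstatement of the B-2.1 goal, and the less-than sign in C-2.0 is a slip or a lost symbol whose intent B-2.1 and B-2.7.1 settle. A site or analyst following the plan would still recruit to 225 completers, analyze every available pair and apply the 0.83 criterion.

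The margin allows 11.1% of completers to lack a pair. Whether actual losses stay below that cannot be judged from the documents, but power at a true r of 0.90 stays above 95% down to 165 pairs. This rests on Fisher's z approximation, a true correlation of 0.90 as the plan assumes, and losses unrelated to the size of the correlation.

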## B- 2.8. Monitoring plan

All case report forms will be 100% monitored.

Each site will have 4 or 5 monitoring encounters

- Site initiation
- After 10-15 subjects have completed the study at a site
- After ~40 subjects have completed the study at a site (for sites with more than 40 complete subjects)
- After all subjects have completed the study at a site
- Study closeout

Note that site initiation and closeout visits may be remotely supported by the monitor. All case report form monitoring will be done on-site. Details of the monitoring plan are described in section E.

## **C. RISK ANALYSIS**

There will be blood draws exclusively for the study at sites using the Staged enrollment plan. There is minor pain from the blood draws. The blood drawing procedure may make some infants and their parents anxious. Both of these risks are transient. A study-specific blood draw is not necessary at the sites using the Simultaneous enrollment plan.

At all sites, there is the risk of loss of privacy from the collection of dates and time of birth, dates and time of blood collection for TSB levels that are ordered clinically, and race and ethnicity information collected for the study. There is also a risk loss of privacy of infants on whom image data are obtained and stored on the study computer server. However, the images will not include identifying information (i.e. the images do not include faces).

### **C-1.0 Minimizing risks**

The risks of the blood draw for TSB levels at Staged enrollment plan sites will be minimized by having the blood obtained by phlebotomist with expertise in drawing blood from newborn infants. A maximum of 1 mL of blood will be obtained from the study participants. Blood samples will be identified only by a subject ID number to ensure privacy.

To minimize the risks from loss of privacy, all study files will be kept in a locked file cabinet in a locked office at each site. The key linking study ID numbers to a particular participant (i.e., the **Study Enrollment Log**) will be kept in a separate locked file cabinet and be kept at the site. This link (with medical record numbers to identify study subjects) will be kept at each site and not provided to the data coordinating center. Image data of study subjects contains only a small amount of skin of the subject's chest; no identifying information is included with the images. Images will be stored on a secure computer server. The data will only be accessible by the technical staff at BiliCam, LLC. Access will be by username and password only.

### **C-2.0 Description of study population**

Overall, a maximum of 375 subjects will be enrolled in the study. A maximum of 150 subjects will be at any Staged enrollment plan site; enrollment will be discontinued at a Staged enrollment plan site when < 75 subjects have completed the study at that site. A maximum of 75 subjects will be enrolled at a Simultaneous enrollment plan site. Enrollment will be discontinued when 225 subjects have completed the study. All subjects will be < 192 hours old. It is anticipated that the number of male and female subjects will be approximately equal.

## **D. DESCRIPTION OF DEVICE**

### **D-1.0 Summary description of the investigational device and its intended purpose**

The BiliCam system is a smartphone application that employs the camera and LED to take images of a newborn's skin that can be used in automated analysis to estimate the bilirubin level in the newborn's blood. The system also comprises a rectangular paper color calibration card that is adhered to the newborn's sternum, with a rectangular hole in the middle, which frames the patch of skin that will be imaged and analyzed. The colors printed on the calibration card are used in the analysis as reference values against environmental variables.

The intended purpose of BiliCam is to be able to use an ordinary smartphone as a transcutaneous bilirubinometer, so that the result may be used by a medical practitioner in screening for neonatal jaundice that may require an intervention such as phototherapy.

#### **D-3.0 Name or number of the model/type, including software version and accessories, if any, to permit full identification**

The mobile device will consist of an iPhone 5S model phone, with an operating system of iOS 10.3.2 and an iPhone 7 model phone with an iOS of 10.3.2 or later.

At the start of the study, BiliCam software app with version 3.0.0 will be preinstalled on the study devices. In the event that it is determined that modifications are necessary for the study to continue, all devices used in the study will be updated with the newer versions. Details of the change and impact will be described in an update to the Data Management Plan.

#### **D-4.0 Description as to how traceability shall be achieved during and after the clinical investigation, for example by assignment of lot numbers, batch numbers, or serial numbers**

The card used for each test will be affixed to the **Study Visit Case Report Form** for each subject after use. The version number of the software, as well as information for each specific phone that the sample was collected with will be recorded in the corresponding metadata file uploaded by the iPhone to the server.

#### **D-5.0 Intended purpose of the investigational device in proposed clinical evaluation**

BiliCam is a non-invasive transcutaneous bilirubinometer, which is intended as an index to predict serum bilirubin levels without regard to race, gender, or bodyweight.

#### **D-6.0 Populations and indications for which the investigational device is intended**

BiliCam is a non-invasive mobile application transcutaneous bilirubinometer which is indicated as an index to predict serum bilirubin levels in neonates > 35 weeks gestational age without regard to gender, race, or bodyweight. BiliCam provides a numerical measurement of predicted bilirubin level in mg/dL within a clinically relevant range that has been correlated with total serum bilirubin. The device is used by healthcare practitioners in the hospital, outpatient or home use environments. Neonates whose BiliCam test results are indicative of hyperbilirubinemia are evaluated by their physician(s) for appropriate patient management. The device is not indicated for use during or after exchange transfusions or phototherapy.

#### **D-7.0 Description of the investigational device including any materials that will be in contact with tissues or body fluids**

A small amount of adhesive on the paper calibration card will be in contact with the neonate's skin on the

sternum; some of the card itself may also rest lightly on the sternum. The adhesive is a hydrogel that has had biocompatibility testing and is currently used on other (non-investigational) high-volume production medical devices for neonates, such as electrodes. The adhesive is water soluble, so may be flushed with a small amount of water if necessary to help reduce adhesion and aid safe removal.

#### **D-8.0 Summary of the necessary training and experience needed to use the investigational device**

Instructions for use of the BiliCam app are shown in appendix 2 and will be reviewed by research staff at each study site. At the site initiation visit, the overall principal investigator will review use of the app on the study mobile phone with research staff, and research staff involved in obtaining BiliCam images will practice using the app, and demonstrate proficiency by obtaining BCB values on phantoms. The research staff at each site will also be taught on how to handle, apply and remove the calibration cards at the site initiation visit.

#### **D-9.0 Description of the specific medical or surgical procedures involved in the use of the investigational device**

No specific medical or surgical procedures are involved in the use of the device.

### **E. MONITORING PROCEDURES**

A CRO will be selected by the Sponsor to oversee the conduct of the trial. An appropriate representative of the CRO (study monitor) will maintain contact with the Investigator and will visit the study site for the purpose of discussing and/or retrieving data. An initiation (pre-study) visit will be made by the Sponsor (under the guidance of the study monitor) to discuss with the site investigator the protocol and the obligations of both the site. The site investigator will allow the study monitor to perform periodic, interim monitoring visits. The purposes of these visits are:

- To verify that written Informed Consent was obtained prior to each subject's participation in the trial.
- To assess the progress of the study.
- To review the compliance with the study protocol.
- To determine whether all adverse events were appropriately reported.
- To determine whether the Investigator is maintaining the essential documents.
- To discuss any emergent problem.
- To check the CRFs for legibility, accuracy and completeness.
- To validate the contents of the CRFs against source documents.
- To photocopy and collect completed CRFs.
- To assess the status of device accountability.

The site investigator will make available the source documents for inspection. This information will be considered as confidential. Violations of and deviations from the protocol must be notified to the study monitor as soon as possible.

The study monitor will perform a closeout visit at the time when all CRFs have been retrieved and all queries have been answered. All monitoring visits will be documented in monitoring reports.

### **E-1.0 Case Report Forms (CRFs)**

CRFs will be provided for each subject. The study monitor will review the forms at each site visit. The appropriate CRFs will be completed for all subjects who sign informed consent, even if the subject fails to complete the study. No section of the CRFs will be left blank without an appropriate explanation by the site investigator, since the lack of such explanation may necessitate discarding an otherwise usable observation. If requested, copies of the CRFs will be made available to the appropriate regulatory agencies.

### **E-2.0 Auditing/inspecting**

The site investigator will make all pertinent records available, including source documentation, for inspection by regulatory authorities and for auditing by the sponsor. This information will be considered as confidential. Audits/Inspections may occur any time from start to after conclusion of the study. When an Investigator signs the protocol, he/she agrees to allow regulatory authorities and sponsor auditors to inspect his/her study records.

### **E-3.0 Archiving of records**

Copies of the protocol, subject identification codes, CRFs, source data, informed consent forms and other documents pertaining to the study conduct will be kept for the maximum period of time as required by the study center. This time period will be at least two years after the last approval of the marketing application of the investigational medical device and until there are no pending or contemplated marketing applications, or at least two years have elapsed since the formal discontinuation of clinical development of the investigational medical device.

No study document will be destroyed without prior written agreement between the Sponsor and the Investigator. Originals of all documentation and copies of outgoing correspondence concerning the study will be stored and retained by the Sponsor in a safe area in the trial files for the lifetime of the product. In particular, the final report sent by the site investigator to the IRB/IEC will be retained by the sponsor, or the subsequent owner, for five years beyond the lifetime of the device.

## **F. MEDICAL DEVICE LABELING**

Every mobile phone assigned to the study used at each study site as well as the envelope containing the calibration cards, will have a label applied indicating that the device is investigational and only for investigational use. A copy of the label is included in appendix 3.

#### I. FORMS AND OTHER DOCUMENTS RELATED TO DATA ENTRY

Other relevant documents are included in appendix 4. These documents are only applicable to the data coordinating center. The documents in appendix 4 include:

- Code keys for CRFs
- Guideline for coding race/ethnicity
